1 TRIAL FLOW DIAGRAM

2 BACKGROUND

2.1 Chronic Myelomonocytic Leukaemia (CMML)

Chronic myelomonocytic leukaemia (CMML) is a myelodysplastic / myeloproliferative neoplasm with a high median age of presentation (75 years) and a poor prognosis; the median survival from diagnosis remains only 11-17 months. The incidence of CMML is poorly defined, although large population-based studies estimate that CMML constitutes approximately 10% of cases of myelodysplastic syndrome (MDS) where the overall incidence of MDS is approximately 4 cases per 100,000 per year and rises to a level of >30 / 100,000 / year beyond the age of 70. Due to its relative rarity, its clinical and morphological heterogeneity and its overlap with other myeloid neoplasms, CMML has been a historically under-researched disease entity, with few clinical studies addressing it in isolation.

CMML has a highly heterogeneous disease phenotype with individual patients showing varying degrees of 'dysplastic' and 'proliferative' disease features. It is characterised by peripheral blood monocytosis (>1x10⁹/l), bone marrow failure and accompanying blood cytopenias, sometimes in association with leucocytosis and other myeloproliferative features such as hepatosplenomegaly, constitutional symptoms and infiltration of the skin and other organs. In 1982, CMML was included as one of five MDS categories within the French-American-British (FAB) classification on the basis of marrow dysplasia, clonal cytogenetic abnormalities and a propensity for progression to acute myeloid leukaemia (AML).⁽⁴⁾ Since 2001, the WHO classification has moved CMML into a separate category of 'mixed myelodysplastic / myeloproliferative neoplasms' where the disease has been additionally sub-divided into CMML-1 (with <10% bone marrow blasts) and CMML-2 (with 10-19% blasts) based on the powerful prognostic weighting of the bone marrow blast count. ⁽⁵⁾ A rare separate entity, the category of 'CMML with eosinophilia' has also been created; this is associated with translocations involving 5q33 (platelet-derived growth factor receptor) and a high degree of therapeutic sensitivity to imatinib mesylate therapy; CMML with eosinophilia is not representative of the bulk of CMML cases and falls outside the scope of the Monocle study.

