3.2.2 Secondary Endpoints

- Incidence and duration of CR / PR / clinical benefit (according to International Consortium MDS/MPN Response Criteria)
- Overall clinical response rate (according to Wattel and modified IWG Criteria)
- Achievement of red blood cell and platelet transfusion independence
- Overall survival
- Progression-free survival
- Incidence of transformation of CMML to AML (and time to AML transformation)
- Duration of tefinostat therapy
- Quality of life
- Biological correlates including hCE-1 expression, changes in protein acetylation

For formal definitions of study endpoints refer to section 10.4.

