10 STATISTICAL CONSIDERATIONS

10.1 Sample size and early stopping rules

Up to 40 patients will be recruited to the study, all of whom will receive tefinostat therapy. The proposed trial design (Bryant and Day)¹⁶⁾ is based on Simon's two-stage design, but incorporates toxicity as well as clinical efficacy (futility) considerations into sample size and early stopping rules.

The primary clinical efficacy objective of the study is to determine overall response rate after 6 cycles of tefinostat. It is felt that if the overall response rate is below 10% the treatment should be rejected, and if above 30% the treatment is sufficiently promising to warrant further evaluation in a phase III trial. These figures reflect the minimum clinically relevant response rate seen in the CMML-201 study of azacitidine therapy in a similar CMML patient population. (17)

The primary safety and tolerability objective is to determine the proportion of patients who suffer an unacceptable level of toxicity as assessed during the first 2 cycles of tefinostat treatment. It is felt that if more than 40% of patients suffer unacceptable toxicity then the treatment should be rejected, and if fewer than 20% suffer some toxicity then the toxicity profile is considered acceptable. A maximum tolerated dose is often defined as the dose at or below the level at which one-third of patients experience toxicity and these figures correspond to that definition.

The significance level for both the efficacy and tolerability endpoints was chosen to be 10%. This is the bound of probability of recommending a treatment with either inadequate efficacy or unacceptable safety. The two-stage design was chosen to allow for early termination in the event of unacceptable toxicity or lack of efficacy. Under these conditions, and setting power at 85% for both the efficacy and safety endpoints, a maximum of 40 evaluable patients need to be recruited into the study. The first stage will recruit up to 19 patients and will require 6 or fewer to have unacceptable toxicity, with at least 3 patients showing clinical benefit (as defined in section 8.3) in order to proceed to the second stage.

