10.2 Data analysis

Statistical analysis will be overseen by [name], Professor of Translational Statistics at Cardiff University and CTR Lead. Analysis will be descriptive for the defined primary and secondary endpoints of the trial (proportions of patients with response/toxicity). The analysis population (patients evaluable for the primary endpoints) will include any patient starting one cycle of tefinostat therapy.

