10.4.2 Secondary outcome measures

- Incidence of CR / PR / clinical benefit will be defined according to the International Consortium MDS/MPN Response Criteria⁽²⁸⁾ (see Appendix 3) at day 29 of the sixth or last cycle of tefinostat (whichever is the earlier). Duration of response will be measured from the date of investigations confirming the achievement of response until the date on which it is confirmed that the patient is no longer sustaining response.
- Overall clinical response rate according to Wattel and Modified IWG criteria (see Appendix 4 and 5).
 Responses will be defined as the cumulative proportion of patients achieving minor response of better (according to Wattel criteria⁽¹⁴⁾ and/or haematological improvement or better (according to the Modified IWG criteria)⁽²³⁾ at day 29 of the sixth or last cycle of tefinostat (whichever is the earliest).
- Red blood cell transfusion independence will be deemed to have been achieved if a patient who
 received red cell transfusion support in the eight weeks prior to baseline assessment remains free
 from red cell transfusion for a period of ≥ eight weeks
- Platelet transfusion independence will be deemed to have been achieved if a patient who received
 platelet transfusion support in the eight weeks prior to baseline assessment remains free from
 platelet transfusion for a period of ≥ eight weeks
- Overall survival is defined as the time from the date of trial registration to the date of death from any
 cause. Patients discontinuing the study, lost to follow-up or still alive at the end of study will be
 censored at the date of last follow-up.
- Progression-free survival is defined as the time from date of trial registration to the date of progression
 or death from CMML. Patients who die from a cause other than CMML prior to progression will be
 censored in the analysis. The date of progression is the date of the decision to investigate a clinical
 suspicion of progression which is subsequently confirmed.
- Time to AML transformation of CMML is defined as the time from trial registration to AML transformation of CMML or last follow-up. Patients in whom CMML does not transform to AML will be censored at the last date they were known to be alive and free from AML transformation of CMML. The date of AML transformation of CMML is the date of the decision to investigate clinical suspicion of AML transformation which is subsequently confirmed.

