10.5 End of trial definition

Patients will be followed up for a minimum of 18 months (to assess overall survival and progression free survival) following registration, or for 30 days after the last trial treatment if this exceeds 18 months. The end of trial will be 6 months after the last data capture. This will allow sufficient time for the completion of protocol procedures, data collection and data input. CTR will notify the MHRA and main REC that the trial has ended and will provide them with a summary of the clinical trial report within 12 months of the end of the trial.

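### Time to AML transformation censors AML-free deaths, so an AML incidence read from that curve would be overstated; death without AML should be a competing event

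*Protocol*

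**What the plan says.** The synopsis and section 3.2.2 list one secondary endpoint with two parts: "Incidence of transformation of CMML to AML (and time to AML transformation". Section 3.2.2 refers the reader to section 10.4 for formal definitions. Section 10.4.2 defines only the time part: "Time to AML transformation of CMML is defined as the time from trial registration to AML transformation of CMML or last follow-up". The censoring rule follows: "Patients in whom CMML does not transform to AML will be censored at the last date they were known to be alive", the sentence going on to add that they must also be free of transformation at that date. Death is neither an event nor an exception to the censoring, and nothing elsewhere in the protocol treats it as a competing event.

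On method, section 10.2 says only: "Analysis will be descriptive for the defined primary and secondary endpoints of the trial". It names no estimator for AML.

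On mortality, section 2.1 describes a disease "with a high median age of presentation (75 years) and a poor prognosis" and states that "the median survival from diagnosis remains only 11-17 months". Section 10.5 sets the horizon: "Patients will be followed up for a minimum of 18 months".

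**The concern.** A patient who has died can no longer transform. Kaplan-Meier treats a censored patient as still at risk of AML after leaving, with the same future risk as those who remain. Applied to deaths, one minus Kaplan-Meier estimates the AML risk that would be seen if nobody died first. That is not the incidence patients experience, and it is always at least as large.

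The gap is small when few patients die AML-free and large when many do. The protocol's own survival and follow-up figures point to many. The trial has a single arm, so no internal comparison would cancel the excess. An inflated figure would stand in the report as the transformation rate on tefinostat.

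**Working it through.** **1. Plan's own figure.** The protocol gives no AML rate, so there is none to reproduce. Its computed design does reproduce and does not involve AML. Taking response and toxicity as independent, power is 0.941 × 0.911 = 0.857 against the stated 85%.

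**2. Inputs from the protocol.** Median survival 11-17 months from diagnosis (section 2.1); follow-up at least 18 months from registration (sections 4.3 and 10.5).

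**3. Assumptions.** Constant hazards; survival from registration like survival from diagnosis; AML-free death hazard equal to 70% of the hazard implied by median survival; true 18-month AML incidence of 25% or 15%.

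**4. Mortality by 18 months.** 1 − 0.5^(18/median) gives 68%, 59% and 52% for medians of 11, 14 and 17 months.

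**5. Formulas.** Let d be the AML-free death hazard and a the AML hazard, per month.

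- d = 0.7 × ln 2 / median
- True incidence at 18 months = a/(a+d) × [1 − exp(−18(a+d))]; solve for a
- One minus Kaplan-Meier with deaths censored = 1 − exp(−18a)
- Share of patients without AML who are dead by 18 months = d/(a+d) × [1 − exp(−18(a+d))] / (1 − true incidence)

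**6. Worked case: median 14 months, true incidence 25%.** d = 0.7 × 0.6931/14 = 0.03466. Solving gives a = 0.02219. Check: 0.02219/0.05685 × [1 − exp(−1.023)] = 0.390 × 0.641 = 0.25. The curve reads 1 − exp(−0.3994) = 0.329. The share dead is 0.610 × 0.641 / 0.75 = 0.521.

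**7. All six cases.**

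| Median survival (months) | True incidence | One minus Kaplan-Meier | AML-free patients dead by 18 months |
|---|---|---|---|
| 11 | 25% | 35.2% | 61.0% |
| 14 | 25% | 32.9% | 52.1% |
| 17 | 25% | 31.5% | 45.3% |
| 11 | 15% | 21.4% | 58.2% |
| 14 | 15% | 19.9% | 49.5% |
| 17 | 15% | 19.0% | 43.0% |

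**8. Varying the 70%.** At 40%, a true 25% reads as 29-31% and 27-41% of AML-free patients die by 18 months. At 100%, a true 25% reads as 34-40% and 55-74% die. The direction does not change.

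**9. Second model.** Let the 11-17 month median describe overall survival including deaths after AML, with an assumed 4-month median survival after transformation. For true incidences of 10-30%, the curve reads 1.22 to 1.60 times the truth; a true 20% reads as 26-31%.

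**10. Simulation.** In 20,000 simulated trials of 40 patients (true incidence 20%, median time to AML-free death 14 months, complete 18-month follow-up), mean one minus Kaplan-Meier was 29.5%. The mean crude proportion was 20.1%.

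**The case against.** The strongest reply is that the protocol never says it will use one minus Kaplan-Meier for AML incidence. Analysis is descriptive, the censoring rule sits under the time variable, and the choice of estimator commonly belongs in the SAP. With 40 patients and good expected follow-up, incidence could be a simple proportion, which step 10 shows is not inflated. Censoring at AML-free death is also the correct setup for a cause-specific hazard. All of this stands. A reader might infer that the reported incidence is bound to be too high; the protocol does not support that, and the overstatement is conditional on reading incidence from the curve.

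A reader might also infer that most AML-free patients will leave by dying. Under the 70% assumption that holds in only three of the six cases, so roughly half is the fair statement. That death is the main competing event is likewise an inference from poor survival. Nor does the protocol plan a comparison of its AML figure with other cohorts, so no harm of that kind can be charged to it.

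On size, 10 AML cases in 40 patients would carry an exact 95% CI of about 13% to 41%, wider than the assumed shift of 6-10 points. That limits the practical weight. It does not excuse a systematic error that costs almost nothing to remove.

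The reply does not dispose of the stated rule. Section 3.2.2 sends the reader to section 10.4 for definitions, and the only one there censors deaths. A SAP that adopted cumulative incidence would have to depart from that rule.

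**Conclusion.** The point holds in conditional form. Section 10.4.2 censors patients who die without AML and supplies the only formal definition behind the AML incidence endpoint. If incidence is read from that curve, it will be overstated. Under constant hazards and the 70% assumption, a true 18-month incidence of 25% reads as about 31-35% and 15% as about 19-21%. Across the alternative assumptions in steps 8 and 9 the overstatement ranges from about 1.1 to 1.6 times (for example 28.6/25 = 1.14 at a 40% death share and a 17-month median).

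These sizes rest on assumed AML rates and death hazards. The survival median is from diagnosis, whereas the trial clock starts at registration and previously treated patients may enter. The direction rests only on some patients dying AML-free.

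The correction should be made, but it is not critical. The endpoint is secondary and descriptive, and the decision rule in section 10.1 uses only response and toxicity.

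**What to change.** In section 10.4.2, state that death without AML is a competing event for AML transformation and that only patients alive and AML-free at last contact are censored. Define AML incidence as a cumulative incidence function (Aalen-Johansen) with 95% CI; the reporting times can be left to the SAP. If the death-censored analysis is wanted, keep it and label it as a cause-specific hazard, not as incidence.

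The cost is a sentence or two. Section 11.6 already collects the date and cause of death, and the section 8 schedule monitors AML transformation from registration to the end of the trial. No new data, patients or visits are needed, and standard software does the estimation.

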10.5 End of trial definition

Patients will be followed up for a minimum of 18 months (to assess overall survival and progression free survival) following registration, or for 30 days after the last trial treatment if this exceeds 18 months. The end of trial will be 6 months after the last data capture. This will allow sufficient time for the completion of protocol procedures, data collection and data input. CTR will notify the MHRA and main REC that the trial has ended and will provide them with a summary of the clinical trial report within 12 months of the end of the trial.

11 PHARMACOVIGILANCE

The collection and reporting of Adverse Events (AEs) will be in accordance with the Medicines for Human Use Clinical Trials Regulations 2004 and its subsequent amendments. Definitions of different types of AE are listed below. Investigators should assess the seriousness and causality (relatedness) of all SAEs experienced with reference to the Investigator's Brochure. Investigators at participating centres are obliged to report severe adverse events (SAEs) that occur in this trial to CTR in a timely manner.

11.1 Definitions of adverse events

11.1.1 Adverse event (AE)

An adverse event (AE) is any unintentional, unfavourable medical occurrence in a clinical trial subject which does not necessarily have a causal relationship with study treatment. This includes:

- new clinical signs or symptoms
- new illnesses or diseases (or the deterioration of an existing disease or illness)
- new clinically relevant deteriorations in any laboratory assessments or clinical tests

11.1.2 Adverse reaction (AR)

An adverse reaction (AR) is an untoward and unintended response to any dose of IMP administered, judged by either the reporting investigator or sponsor as having 'reasonable causal relationship' to the IMP

11.1.3 Serious adverse event (SAE)

A serious adverse event (SAE) is defined as an untoward (unfavourable) medical occurrence which is:

- Fatal or life-threatening*
- Requires or prolongs hospitalisation
- Is significantly or permanently disabling or incapacitating
- Constitutes a congenital anomaly or birth defect
- May jeopardise the patient and may require medical or surgical intervention to prevent one of the outcomes listed above
- Development of a non-haematological toxicity of grade 3 (as defined by Common Terminology Criteria for Adverse Events (CTCAE) version 4 (see Appendix 8), which does not resolve to grade 2 or less within 7 days
- Development of any grade 4 non-haematological toxicity

*The term 'life-threatening' in the definition of a SAE refers to an event in which the patient was at risk of death at the time of the event; it does not refer to an event which hypothetically might have caused death if it was more severe.

The following events will **not** be recorded as SAEs within this trial:

- Hospitalisation for routine treatment or monitoring of CMML or other pre-existing condition that is
 not associated with any deterioration of the condition, for elective or pre-planned treatment
 including surgery or for social care
- Treatment on an emergency outpatient basis for an event not fulfilling any of the definitions for serious as detailed above and not resulting in hospital admission
- Disease progression and/or death due to disease progression
- Deaths attributable to CMML beyond 30 days of the last administration of the study agent

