10.4 Definition of outcome measures

10.4.1 Primary outcome measures

- Safety and tolerability of tefinostat will be defined as the proportion of patients experiencing a CTC grade 3-4 non-haematological toxicity⁽²⁵⁾ or death during the first two cycles of tefinostatthat is judged by either the principal investigator or the chief investigator (or his delegate) as having a reasonable suspected causal relationship to tefinostat.
- Overall clinical response rate will be defined as the cumulative proportion of patients achieving clinical benefit (or better) according to International Consortium MDS/MPN Response Criteria⁽²⁸⁾ at day 29 of the sixth or last cycle of tefinostat (whichever is the earliest).

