11.2.2 Serious adverse events

SAEs should be monitored from the time of patient registration until 30 days following the last administration

of protocol treatment. On becoming aware that a patient has experienced an AE defined as serious (see

11.1.3), the event should be reported on a SAE form. The investigator (or delegate) must complete, date and

sign the form which should be emailed (or faxed if email is not possible) to CTR using the contact details listed

below within 24 hours of first becoming aware of the event. Please ensure that multiple events are not

combined into one SAE form.

SAE Email: [contact]

SAE [contact]

When completing the form, the investigator will be asked to define the causality and severity of the SAE which

should be documented using CTCAE version 4. They will not be asked to define expectedness, this will be

carried out by the clinical reviewer.

It is accepted that a causality assessment is not always available at the time of the initial report – this opinion

should be provided as soon as possible to ensure that regulatory reporting timelines are met.

Investigators should also report SAEs to their own Trust in accordance with local practice. All SAEs should be

followed up until resolution or stabilisation of the event.

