11.6 Deaths

Deaths must be reported as an SAE within 24 hours of becoming aware of the event if they meet the criteria outlined in 11.1.3 above. The date and cause of death will be collected. All deaths must also be recorded on the death report form, this information will also be collected in trial CRFs.

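### The two SAE exclusions in section 11.1.3 conflict for CMML or progression deaths within 30 days of the last dose, and no section ensures that the chief investigator promptly judges causality for these deaths

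*Protocol*

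**What the plan says.** Protocol section 11.1.3 ends with events that are not to be recorded as SAEs. Two of them concern deaths from the disease:

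- "Disease progression and/or death due to disease progression", with no time limit;
- "Deaths attributable to CMML beyond 30 days of the last administration of the study agent".

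Section 11.2.2 sets the window for SAE surveillance: "SAEs should be monitored from the time of patient registration until 30 days following the last administration" of protocol treatment. Section 11.6 says: "Deaths must be reported as an SAE within 24 hours of becoming aware of the event if they meet the criteria outlined in 11.1.3 above". It adds a second route: "All deaths must also be recorded on the death report form, this information will also be collected in trial CRFs".

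The primary toxicity endpoint in section 10.4.1 counts patients who, in the first two cycles, have a grade 3-4 non-haematological toxicity or a death "judged by either the principal investigator or the chief investigator (or his delegate) as having a reasonable suspected causal relationship to tefinostat". Section 11.3 starts central review when the trials office receives an SAE form. It names seriousness and expectedness as what the reviewer determines, and it classes an SAE as a serious adverse reaction on the local investigator's judgement of causality.

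**The concern.** Take a patient who dies on treatment, or within 30 days of the last dose, and whose death the site attributes to progression of CMML. Under the first exclusion this is not an SAE. Under the second it is, by implication, because CMML deaths are exempt only after 30 days. Two sites could handle the same death differently, and both could point to the protocol.

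A death that generates no SAE form skips the 24-hour report, the causality entry that section 11.2.2 asks for on that form, and the central review of section 11.3. Section 10.4.1 lets the chief investigator count a death as related even when the site does not. That safeguard works only if the chief investigator sees the case.

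Attribution is a real judgement here. The trial has one arm, section 4.1 puts prior experience in CMML at two patients, and section 2.1 gives a median survival from diagnosis of 11-17 months. If a drug-related death were missed, the recorded toxicity rate would fall. The notification to the IDMC under section 10.3, which depends on a death being known as treatment-related, could also come late or not at all.

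**Working it through.** **Step 1: the texts side by side, for a death the site calls progression.**

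| Time of death | Unlimited exclusion (11.1.3) | 30-day exclusion (11.1.3) | Death reporting (11.6) |
|---|---|---|---|
| Within 30 days of last dose | Not an SAE | Not exempt, so an SAE by implication | Refers back to 11.1.3: undetermined |
| Beyond 30 days | Not an SAE | Not an SAE | No SAE report |

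The bullets disagree only in the first row. That row lies inside the SAE window of section 11.2.2, and it includes on-treatment deaths in cycles 1-2.

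**Step 2: other routes to the chief investigator.** The death report form and the CRFs record date and cause for every death (11.6), but no deadline or causality review is attached to the form, and section 9.1 does not list it. Form F is due within 14 days of stopping therapy (9.1), again with no causality review attached. Section 11.3 starts from an SAE form and does not name causality. The data therefore reach the trials office, but no section assigns a prompt central causality judgement on them.

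**Step 3: reproduce the design.** Inputs from section 10.1: stage 1 of 19 patients, continuing with at most 6 toxicities and at least 3 responses; final success with at least 7 of 40 responses and at most 12 of 40 toxicities; toxicity rates 20% and 40%; response rates 10% and 30%; error bound 10%; power 85%.

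For a recorded toxicity rate q, the chance of passing both toxicity limits is

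T(q) = sum over x = 0 to 6 of P[Bin(19, q) = x] × P[Bin(21, q) ≤ 12 − x].

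For a response rate p, the chance of passing both response limits is

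E(p) = sum over x = 3 to 19 of P[Bin(19, p) = x] × P[Bin(21, p) ≥ 7 − x].

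Results: T(0.20) = 0.911, T(0.40) = 0.103, E(0.10) = 0.080, E(0.30) = 0.941. Taking response and toxicity as independent:

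- response 10%, toxicity 20%: 0.080 × 0.911 = 0.073;
- response 30%, toxicity 40%: 0.941 × 0.103 = 0.097;
- response 30%, toxicity 20%: 0.941 × 0.911 = 0.857.

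The first two are within the 10% bound and the third exceeds 85%. The stated design reproduces.

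**Step 4: illustrate missed cases.** The protocol gives no miss rate, so those below are assumptions. At a true rate of 40%, 0.40 × 40 = 16 patients have toxicity. Missing 5% of these (16 × 0.05 = 0.8 patients) gives a recorded rate of 0.40 × 0.95 = 0.38. Missing 10% (1.6 patients) gives 0.40 × 0.90 = 0.36.

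| Assumed share of toxicity cases missed | Recorded rate | Pass toxicity rules alone | Pass full rule, response 30% | Pass full rule, response 10% |
|---|---|---|---|---|
| 0% | 0.40 | 10.3% | 9.7% | 0.8% |
| 5% | 0.38 | 15.4% | 14.5% | 1.2% |
| 10% | 0.36 | 22.1% | 20.8% | 1.8% |

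As a cross-check, suppose exactly one case goes uncounted. Moving only the final toxicity limit from 12 to 13 gives 15.1%. Moving both limits by one (7 of 19 and 13 of 40) gives 18.7%.

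**The case against.** The strongest reply is that both bullets are exclusions, so an event that meets either is simply not an SAE. On that reading, progression deaths are always exempt, and other CMML deaths only after 30 days. Progression also has formal criteria in Appendix 3, and section 10.4.2 names progression and death from CMML separately. This is a possible reading, and the conflict does arise by implication. But section 11 never draws the distinction, and sites report from section 11. Even on that reading, an on-treatment death labelled progression generates no SAE form.

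A reader might infer that such deaths drop out of the primary toxicity count. The documents do not support that. The endpoint does not use SAE status, and adverse events are collected until 30 days after the last dose (11.2.1). All deaths are recorded, and the chief investigator remains free to judge any of them. A case is lost only if the death was truly drug-related, fell in the first two cycles, was labelled progression by the site, was not picked up by the chief investigator, and came without any other counted toxicity.

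A reader might also infer that an SAE form would by itself secure a central causality judgement. Section 11.3 does not say so. Likewise, the IDMC trigger in section 10.3 is notification of a treatment-related death, not receipt of an SAE form, so a death the site judges unrelated would not meet it on a form either unless someone overrode the site.

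Finally, the miss rates have no source in the protocol. The completed phase I study offers no support for frequent toxic deaths: all 18 patients completed the first cycle, with no dose-limiting toxicity (Appendix 12). That stands, and it is why the figures are only an illustration.

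**Conclusion.** The inconsistency is real and should be reconciled. For CMML or progression deaths within 30 days of the last dose, section 11.1.3 gives two answers and section 11.6 chooses neither. The direct effect is uneven 24-hour reporting. The effect on the primary toxicity count is indirect, and it comes as much from the absence of a named central causality step as from the exclusions.

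No stated design figure is wrong. The decision rule is, however, sensitive to small losses: with 5% or 10% of toxicity cases assumed missed at a true 40% rate, the chance of passing the toxicity rules alone moves from 10.3% to 15.4% or 22.1%. These figures show what about one or two missed patients would do. They do not estimate how often it would happen, and the full-rule figures also assume that response and toxicity are independent.

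**What to change.** Make three linked wording changes.

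1. In section 11.1.3, give the exclusion of deaths due to progression the same 30-day limit as the CMML-death bullet. Every death within 30 days of the last dose is then SAE-reportable whatever its presumed cause. Non-fatal progression can stay excluded.
2. In section 11.6, say the same directly, so that the 24-hour rule does not rest on interpreting the list.
3. In section 11.3, state that for every death in the first two cycles the chief investigator or delegate judges causality, in addition to seriousness and expectedness. Changing the bullets alone would not deliver this.

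The cost is a short amendment, a few extra SAE forms and a small number of central reviews. The design, sample size and decision limits do not change.
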